**Figure 1: Pure-Vu Workstation – General design & components**

A detailed description of the system components, its principles of operation, dimensions and packaging is elaborated in the Instruction for use (IFU).

Document title:	Document No.	Version	Page 15 of 61
Optimizing the Preparation Regime Prior to Colonoscopy Procedure with Pure-Vu System	CL00042	1.0	

### 6.1.1 Work Station (WS)

The WS controls the flow of gas (e.g. air) and water or saline to the Oversleeve device and the evacuation of fecal matter and fluids out of the body. The WS has four main functions:

- **Cleansing:** Creates an irrigation stream, which is a mixture of liquid (water or saline) and air into the colon to break up fecal matter. The irrigation of air and liquid (water or saline) is referred to as “cleansing jets”. The cleansing has three modes, high, medium and low with medium being the default setting. The physician can operate the system as per his clinical judgment. It is important to note that the evacuation function noted below is active during cleansing so that fluid is input and removed from the colon simultaneously.
- **Evacuation:** Removes fecal matter and fluids out of the colon. The evacuation function is active during the cleansing as previously noted and can also be used independently. During evacuation the system senses the pressure in the evacuation channel of the Oversleeve and if the pressure goes below pre-set limits will automatically reverse the flow to purge a potential blockage and then switch back to continue evacuation. The user also has the ability to manually purge the evacuation channel as well.
- **User interface:** Consists of actuators and indicators on the WS itself as well as a foot pedal to activate the main functions of the system so that users’ hands are free to manipulate the colonoscope in a standard fashion.

**Oversleeve** The Oversleeve is mounted on top of the colonoscope and is connected to WS via the WS Connector. The Add-on includes the following main components:

- **Tubing:** Six (6) tubes (2 Pebax and 4 PVC) that support the irrigation, evacuation and sensing functions of the system.
- **Cleansing and Evacuation head:** The Oversleeve’s distal part which contains irrigation ports, evacuation openings, and colon sensing port.

Document title:	Document No.	Version	Page 16 of 61
Optimizing the Preparation Regime Prior to Colonoscopy Procedure with Pure-Vu System	CL00042	1.0	

- Inner sleeve: This sleeve attaches the Oversleeve to the colonoscope along its length. This sleeve is inflated to allow the colonoscope to be inserted through it and then deflated to hold onto the colonoscope when it is navigated through the colon. The inner sleeve is also attached to the outer sleeve noted below on one side.
- Outer sleeve: This sleeve covers the entire portion of the device that goes inside the colon keeping the tubes in position and providing a smooth surface to interface with the wall of the colon. The distal 28 cm of the sleeve is coated with hydrophilic coating to provide a lubricious surface to aid in advancing the system through the colon.
- Inflation connector: Provides the port to pressurize the inner sleeve during the loading of the colonoscope and provides the entry location for the colonoscope to be inserted into the Oversleeve.

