## Statistics

Primary Endpoint Analysis	
The primary endpoint is the rate of adequate bowel cleansing level, as determined by Boston Bowel Preparation Scale (BBPS), assessed per patient in both study arms.
 
Chi-square or Fisher's exact test, as appropriate, will be performed in order to compare the proportions of good or excellent cleansing level (i.e., BBPS>1 in all colon segments) post cleansing procedure between the two study arms.

Secondary Analyses	
Cecum intubation rate
 
Proportion tests (Chi-square or Fisher's exact) will be performed in order to compare between the two preparation procedures cecum intubation rate
 
Time analysis
 
T-tests for continuous variables will be performed in order to evaluated the difference between Prep A and Prep B for the following:
 

• Total procedure time

Document title:  Optimizing the Preparation Regime Prior to Colonoscopy Procedure with Pure-Vu System	Document No.  CL00042	Version  1.0	Page 11 of 61
---	------------------------------------	---------------------------	------------------

	

• Time to cecum

 
Safety analysis
 
Individual listings of adverse events including type of device, adverse events (reported term) start date, duration, and severity will be provided.

Determination of Sample Size	This is a pilot study that will include up to 100 patients; no statistical considerations were made to determine the sample size.
Interim analyses	No Interim analysis is planned.

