## 6.3 Clinical data to Date

The latest Pure-Vu System tested in ninety-seven subjects (54% males) from five sites using similar protocol.

Pure-Vu was used in subjects with a partially prepped receiving a colonoscopy for screening, diagnostic or surveillance.

To ensure an inadequately prepped colon subjects underwent a reduced preparation consisting of dietary restrictions (no dried fruit, seeds or nuts) starting 2 days prior to the colonoscopy, an 18 to 24 hour clear liquid diet and a split dose of 20mg Bisacodyl.

The cleansing quality was evaluated before and after use of the Pure-Vu System with the Boston Bowel Preparation Score (BBPS) (1).

Two patients were excluded from the analysis due to the followings:

Document title:	Document No.	Version	Page 18 of 61
Optimizing the Preparation Regime Prior to Colonoscopy Procedure with Pure-Vu System	CL00042	1.0	

- One patient who had breakfast on day of procedure was excluded from the cleansing efficacy and usability analysis due to non-compliance with the pre-procedural prep regimen.
- In one patients the device could not reach beyond the sigmoid colon due to the patient's anatomy, thus the physician used a slim colonoscope to complete the procedure and indicated that only a slim colonoscope would be able to advance past the sigmoid and into the cecum.

The Pure-Vu significantly increased the number of subjects with an adequate cleansing level (BBPS  $\geq 2$  for all 3 colon segments) from 25%; CI 95% [17%, 35%] at baseline to 99%; CI 95% [94%, 100%] after Pure-Vu. Cecum intubation rate was 98%; CI 95% [94%, 100%]). Mean post-treatment BBPS score was  $8.7 \pm 1.0$  vs.  $3.9 \pm 2.2$  prior to Pure-Vu use. Physicians were satisfied with the device's use. No major difficulties were experienced when performing polypectomy and no serious adverse events were reported.

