## 7.0 Risk/Benefit Analysis

### 7.1 Anticipated Risks Associated with Pure-Vu System conjunction with a standard colonoscope

The Pure-Vu is used in conjunction with a standard colonoscope during a colonoscopy procedure. Hence, the complications associated with using the Pure-Vu are anticipated to be similar to those associated with the colonoscopy procedure. As with any colonoscopy procedure, when using the Pure-Vu there is some risk of bowel perforation, pain, infection and bleeding. Although the risks of the procedure with the Pure-Vu System are expected to be comparable to conventional colonoscope (0.35%), the device is an Oversleeve to a standard colonoscope. Hence, diameter is bigger, and the cleansing time may add some minutes to the procedure time. a potential risks associated with the participation in the clinical investigation may include a repeated colonoscopy procedure as the subjects enrolled to the study are required to undergo a limited prep as compared to the preparation given prior to standard colonoscopy procedure.

The latest Pure-Vu version was tested in an animal study including 35 pigs and in preliminary clinical studies including 97 subjects.

Document title:	Document No.	Version	Page 19 of 61
Optimizing the Preparation Regime Prior to Colonoscopy Procedure with Pure-Vu System	CL00042	1.0	

No major complication or serious adverse events occurred within the course of those studies.

In addition, these clinical studies demonstrated an excellent cleansing effectiveness; Pure-Vu improved the cleansing level from 25% at baseline to 99% after the cleansing was operated and in 98% of the patients the cecum was reached and the procedures completed successfully. Efficacy results support the study design rationale that decreases the risks associated with the preparation without increasing the risk related to incomplete/ repeated colonoscopy procedure.

Lastly, patients to be enrolled to this study shall be eligible to colonoscopy, thus the risks detailed above covers all the population intended to participate in the study.

Considering the residual risks and the potential and the risk against benefit assessment, it can be concluded that the system may offer potential benefit to the patients along with no significant risk increase.

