## 7.3 Residual risk associated with the investigational device

The residual risk is the risk remaining after the risk controls have been implemented.

The residual risk is evaluated according to the following:

- Acceptable Residual risk includes all RPN  $\leq 9$ .
- Risks rated 10-16 will be acceptable if the risk benefit ratio justifies it.

All risks of using Pure-Vu were mitigated by risk management process according to EN ISO 14971:2012.

Document title:	Document No.	Version	Page 20 of 61
Optimizing the Preparation Regime Prior to Colonoscopy Procedure with Pure-Vu System	CL00042	1.0	

The mitigation to the risks associated with the investigational device includes but is not limited to the followings:

- Smooth head shape that contains lumens for cleansing jets and evacuation. The lumens' size were optimized to ensure the safety of the patients along with effective cleansing.
- The Pure-Vu Oversleeve are made from a flexible and low friction material to allow ease advancement through the colon and to minimize any impact to the steering angle of the colonoscope.
- Hydrophilic coating at the distal 30cm of the outer sleeve to create a lubricious surface to allow ease insertion and advancement.
- Cleansing procedure can be operated in 3 modes (low, medium, high), where the physician can control the intensity of cleansing jets to ensure the safety of the patients along with effective cleansing.

The potential residual risk following the mitigations are all acceptable (for more details please refer to "Risk analysis report").

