#### **11.1.2 Randomization**

Randomization in blocks will be applied for each site to allocate patients to one of two different bowel preparation regimens (Prep A versus Prep B). The study will utilize randomization in blocks using the standard envelope procedure, which will be applied in order to allocate patients into two arms:

- Group 1 - Will go through the Prep A procedure
- Group 2 - Will go through the Prep B procedure

The site randomization plan will be provided to the study coordinator prior the study start. No blinding is applicable in this study.

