### **12.3 Primary Endpoint Hypothesis Analysis**

The primary endpoint is the rate of adequate bowel cleansing level after the use of the Pure- Vu.

The rate of adequate cleansing level in each colon segment before and after use of Pure-Vu will be evaluated using the Boston Bowel Preparation Scale (BBPS).

A score of 0 - 3 will be given to each of the 3 segments of the colon (Descending, Transverse and Ascending).

Document title:	Document No.	Version	Page 30 of 61
Optimizing the Preparation Regime Prior to Colonoscopy Procedure with Pure-Vu System	CL00042	1.0	

BBPS scores will be rated by the endoscopist, on the basis of three segment scores summed for maximum score of 9, where:

- 0 = unprepared
- 9 = completely clean (in completed to Cecum procedures)

*An adequate cleansing procedure is defined as when all 3 colon segments are graded as 2 or 3.*

Chi-square or Fisher's exact test, as appropriate, will be performed in order to compare proportions of good or excellent cleansing level between the two preparation procedures.

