## 24.0 Appendix F – Case Report Form (filled-in by the physician)

**Site No.      Subject No.      Subject Initials**

Study arm:  Magnesium Citrate 10 oz  Magnesium Citrate 15 oz

**Physician Name:** \_\_\_\_\_

Date subject signed the informed consent form: \_\_\_\_ / \_\_\_\_ / \_\_\_\_  
DD MM YY

Date investigator/designee signed the informed consent form: \_\_\_\_ / \_\_\_\_ / \_\_\_\_  
DD MM YY

Did the subject satisfy all enrollment criteria?  Yes  No (if No, please specify which criterion was not met)

**Patient Gender / Age:** \_\_\_\_\_ / \_\_\_\_\_

**Patient Height (cm) / Weight (kg):** \_\_\_\_\_ / \_\_\_\_\_

Please check all indications that apply for the patients' colonoscopy	Please Check
Screening	
Bleeding	
Polyp surveillance	

CONFIDENTIAL

Document title:  Optimizing the Preparation Regime Prior to Colonoscopy Procedure with Pure-Vu System	Document No.  CL00042	Version  1.0	Page 57 of 61
---	------------------------------------	---------------------------	---------------

IBD surveillance	
Family history (1st degree relative)	
Anemia	
Other: Please specify	

Prescribed Prep	Completed Yes / No
Magnesium Citrate 10oz:	
Magnesium Citrate 15oz:	

	HH : MM
Colonoscopy start time	
Time cecum reached	
Time colonoscopy ended	

Please rate the bowel prep	BBPS Rating Prior to Use of Pure-Vu (0 - 3)	BBPS Rating After Use of Pure-Vu (0 - 3)
Descending colon		
Transverse colon		
Ascending colon		

Comments: \_\_\_\_\_

Document title:  Optimizing the Preparation Regime Prior to Colonoscopy Procedure with Pure-Vu System	Document No.  CL00042	Version  1.0	Page 58 of 61
---	------------------------------------	---------------------------	------------------

	Sigmoid / Descending	Transverse	Ascending
If the cecum was not reached during the colonoscopy procedure, please indicate the furthest anatomical landmark reached			

If cecum not reached, please indicate the reason	Please Check
Poor bowel cleanliness	
Patient intolerance / discomfort	
Clinical and anatomical (such as stricture, redundant colon, etc.)	
Other: Please specify	
_____	
_____	
_____	

Usability	Excellent	Good	Acceptable	Difficult	Unacceptable
Ease of colonoscope advancement with Pure-Vu					
Ease of navigating colonoscope with Pure-Vu					
Torque ability of colonoscope with Pure-Vu					
Ease of sigmoid passing					
Ease of retroflex					

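### The arms are compared on BBPS after discretionary cleansing, but cleansing effort has no CRF field and no between-arm test of pre-cleansing BBPS is clearly specified

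*Protocol*

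**What the plan says.** **Primary comparison.** The synopsis (Statistics, Primary Endpoint Analysis) tests the proportions with BBPS above 1 in every segment "post cleansing procedure between the two study arms", by chi-square or Fisher's exact test. Section 12.3 opens with the adequacy rate after Pure-Vu use and closes with the same test. Section 9.1 names BBPS both before and after cleansing, and 12.3 says both will be evaluated, but neither clearly states a between-arm test of the score before cleansing.

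**Control of cleansing.** Section 6.1.1 describes three modes, with medium as the default, and adds: "The physician can operate the system as per his clinical judgment". Section 7.3 repeats the point: "where the physician can control the intensity of cleansing jets". The protocol sets no rule on amount or duration. Operating details are referred to the Instructions for Use, which are not shown.

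**What is captured.** Appendix F has BBPS per segment before and after Pure-Vu, the colonoscopy start time, "Time cecum reached", the end time, and an intervention time for each polyp. It has no line for cleansing time, mode or fluid volume. Section 11.1.5 has the examination video-recorded and archived for possible later use, with no planned reading for cleansing.

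**Time outcomes.** Section 12.4 compares time to cecum and total procedure time between arms. Section 7.1 acknowledges that "the cleansing time may add some minutes to the procedure time".

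**Rating.** Section 11.1.2: "No blinding is applicable in this study". Section 12.3: "BBPS scores will be rated by the endoscopist".

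**The concern.** The amount of cleansing responds to the state of the colon. An operator who meets more residue can irrigate longer or harder until the segments score 2 or 3. Prep quality then shows up partly as effort, and the post-cleansing score reflects what effort could not correct.

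The study purpose in the synopsis is to find the best prep for Pure-Vu procedures, and section 12.7 frames the aim as whether Prep B tends to do better than Prep A. If both arms finish near 100% adequate, the primary comparison cannot tell two equivalent preps from two preps of which one needed considerably more cleansing. That distinction matters when choosing a regimen. A later analysis plan cannot recover effort data that were never captured, except approximately from the video.

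**Working it through.** **1. Reproduce the prior figures.** Section 6.3 reports 97 subjects less 2 excluded, so n = 95, with 25% [17%, 35%] adequate before cleansing, rising from that level "at baseline to 99%; CI 95% [94%, 100%] after Pure-Vu". Exact (Clopper-Pearson) intervals:

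- 24/95 = 25.3% (16.9% to 35.2%)
- 94/95 = 98.9% (94.3% to 100.0%)

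Both match the protocol.

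**2. Implied conversion.** Inadequate before: 95 − 24 = 71. Inadequate after: 95 − 94 = 1. Not converted: 1/71 = 1.4%, exact 95% interval 0.04% to 7.6%. This assumes that colons adequate before cleansing stayed adequate.

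**3. How much of a prep difference survives.** If a share r of inadequate colons stays inadequate in both arms, then

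gap after = gap before × r.

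For an assumed 20-point gap before cleansing:

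- r = 1/71: 20 × 0.0141 = 0.28 points
- r = 0.04%: 20 × 0.0004 = about 0.01 points
- r = 7.6%: 20 × 0.076 = about 1.5 points

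**4. Power before and after cleansing.** Assumptions: 50 per arm (half of the 100 in section 12.1), two-sided 5%, Fisher's exact test by full enumeration. Using the rounded percentages, r = 0.01/0.75 = 1.33%, and adequacy after = 1 − (1 − adequacy before) × r. The pre-cleansing rates are illustrations, not protocol figures.

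| Adequate before, A vs B (assumed) | Adequate after (derived) | Power, pre score | Power, post score |
|---|---|---|---|
| 25% vs 50% | 99.0% vs 99.3% | 67% | below 0.01% |
| 25% vs 60% | 99.0% vs 99.5% | 93% | below 0.01% |
| 40% vs 70% | 99.2% vs 99.6% | 83% | below 0.01% |

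At the upper limit r = 7.6%, the first row becomes 1 − 0.75 × 0.076 = 94.3% against 1 − 0.50 × 0.076 = 96.2%, and power on the post score is still only about 1%.

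**5. What the primary test can see.** With 50 per arm and no failures in one arm, the other needs 6 failures for p < 0.05 (p = 0.027; 5 failures give p = 0.056). Fisher power against 99% in the better arm:

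| Other arm, after cleansing | Power |
|---|---|
| 97% | 0.2% |
| 95% | 2.4% |
| 90% | 27% |
| 85% | 64% |
| 80% | 87% |

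**6. Is total procedure time a substitute?** It covers insertion, inspection, cleansing and polyp work together. Polyp time can be subtracted from the Appendix F entries; insertion and inspection cannot be separated from cleansing. For illustration only: 45 per arm (15 per arm at each of 3 sites), a true 3-minute difference, two-sided 5% t-test. The 3 minutes and every SD are assumed; the protocol gives none.

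| Assumed SD (min) | 4 | 5 | 6 | 7 | 8 | 10 | 12 |
|---|---|---|---|---|---|---|---|
| Power | 94% | 80% | 65% | 52% | 42% | 29% | 22% |

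A direct measure of cleansing time gains only in so far as its SD is smaller than that of total time. The direction is plausible; the size of the gain is an input, not a finding.

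**The case against.** The strongest reply is that prep quality is measured. BBPS is scored per segment during insertion, before cleansing (section 11.1.5, Appendix F), and sections 9.1 and 12.3 name it. A reader might infer from the missing CRF fields that cleansing leaves no trace at all, or that a worse prep will be hidden. The documents support neither. The pre-cleansing score, the video, the procedure times and the polyp intervention times are all recorded. What remains is that no between-arm test of the pre-cleansing score is clearly specified, and that cleansing effort itself has no planned measurement.

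A reader might also infer that the two preps will look equal after cleansing. Only a weaker statement holds: they may. The 99% comes from a bisacodyl regimen with an 18 to 24 hour clear-liquid diet and rests on one failure in 71. A post-cleansing gap of 15 to 20 points would still often be detected.

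It is tempting to blame the open-label design. The mechanism does not need it, since a blinded endoscopist would also irrigate a dirtier colon for longer. Lack of blinding bears on the BBPS ratings, not on this argument.

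Finally, the primary objective (section 8.1) is the performance of Pure-Vu under each prep. Adequacy after ordinary use is a legitimate endpoint for that objective, in a pilot that is declared unpowered. This stands, and it is why the primary endpoint should not change. It does not answer the comparative aim in section 12.7.

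**Conclusion.** The point holds as a limited but real gap. The only clearly specified primary comparison between arms is made after a discretionary step that may compensate for a poorer prep, and the extent of that step is neither recorded on the CRF nor planned to be measured. If the prior conversion rate carries over and is equal in both arms, a 20-point difference in prep quality appears as about 0.3 points in the primary endpoint, with a range of about 0.01 to 1.5 from the uncertainty in 1/71. Pre-cleansing differences of 25 to 35 points would be almost undetectable after cleansing, yet would have 67% to 93% power on a score the trial already collects.

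The result rests on transfer from a different prep, equal conversion in both arms, 50 per arm and a two-sided 5% level. The power figures for time outcomes are illustrative only. The Instructions for Use might contain operating rules that narrow the variation in cleansing.

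**What to change.** 1. **Sections 12.3 and 12.4:** add a comparison of the pre-cleansing adequacy rate (all three segments scored 2 or 3) between Prep A and Prep B, as a difference with 95% CI. The data are already on the CRF.
2. **Appendix F:** add, beside the procedure times, total Pure-Vu cleansing time (min), irrigation fluid used (mL, read from the bag) and cleansing mode(s) used. Name cleansing time and irrigation volume as secondary outcomes in the synopsis and section 9.2, and compare them between arms in section 12.4 with 95% CIs.
3. **Interpretation:** state that the post-cleansing comparison will be read alongside items 1 and 2, so that similar final adequacy is not taken alone as evidence that the preps are equivalent.

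The primary endpoint and the physician's freedom to operate the system stay as they are. The cost is three CRF lines, a little extra recording and a few more comparisons, with no added patients or procedures. Two limits remain: cleansing time recorded by site staff will be approximate, and the pre-cleansing score is still rated by the same unblinded endoscopist.

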### **6.1.2 WS Connector**

The disposable WS Connector is mounted onto the front panel of the WS and connects to the irrigation and sensing lines of the Oversleeve.

The WS Connector is slide into the grooves on the WS and once in place the user activates the locking mechanism to hold the WS Connector in place and align the connections to the two sensors and the air source for the irrigation. The user will then place the tubing that is on the proximal side of the WS Connector into for irrigation. The evacuation tubing will form the Oversleeve will be placed into the channels on the WS Connector and then into the pump heads according to its color-coding. Last the user will connect a standard bag of saline or water to the irrigation line and the evacuation line to the recommended waste tank.

